APPENDIX 4 CONTINUED FROM PREVIOUS PAGE

Haematological Relapse:

From CR	Increase in the aberrant serum free light chain concentration to outside the normal range and by a factor of ≥ 2 from that at the time of CR or re-appearance of the original paraprotein
From PR or VGPR:	Increase in the aberrant free light chain concentration by a factor of ≥ 2 from that at the time of PR ($\geq 50\%$ change in ratio away from normal in patients with renal failure) or doubling of the serum paraprotein level (if starting $>5\text{g/L}$) or doubling and increase of serum paraprotein to $>5\text{g/L}$ (if starting $<5\text{g/L}$)

Organ Response:

Heart	Interventricular septal thickness decreased by 2 mm or 10% improvement in ejection fraction or a 30% and 35 pMol/L reduction in NT-ProBNP (only applicable if there is no change or $<25\%$ improvement in renal function) or significant improvement in lateral wall TDI S wave and E/E' ratio
Kidney	50% decrease (at least 0.5 g/day) in 24-hr urinary protein loss (urine protein must be >0.5 g/day pretreatment) without fall in creatinine clearance of $\geq 25\%$ from baseline
Liver	50% decrease in abnormal alkaline phosphatase value or a decrease in liver size radiographically by at least 2 cm
Nerve	Improvement in electromyogram nerve conduction velocity (rare)
Soft tissue	Definite clinical and/or radiographic improvement with associated functional improvement in affected tissue

Organ Progression:

Heart	Interventricular septal thickness increased by >2 mm compared with baseline or 20% decline in ejection fraction
Kidney	50% increase (at least 1 g/day) in 24-hr urinary protein loss to >1 g/day OR Sustained fall in creatinine clearance of $\geq 25\%$ from baseline
Liver	50% increase of alkaline phosphatase from the lowest value
Nerve	Progressive neuropathy by electromyography or nerve conduction velocity
Soft tissue	Definite clinical and/or radiographic deterioration with associated functional deterioration in affected tissue

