6.3.1 Inclusion Criteria

Patients with the following characteristics are eligible for this study:

1. Aged 18 years or greater
2. Diagnosis of systemic AL amyloidosis with
 - i. exclusion of genetic mutations associated with hereditary amyloidosis and immunohistochemical exclusion of AA and TTR amyloidosis as appropriate
 - ii. Amyloid-related organ dysfunction or organ syndrome (see Appendix 2)
3. Measurable clonal disease
4. Clonal relapse after previous chemotherapy or autograft stem cell transplant OR refractory clonal disease to previous chemotherapy or stem cell transplant
5. Capable of providing written, informed consent and willing to follow study protocol
6. Life expectancy \geq 6 months
7. ECOG performance status of 0-2
8. Platelet count \geq $50 \times 10^9/l$
9. Neutrophil count \geq $1 \times 10^9/l$
10. Haemoglobin \geq 8g/dL
11. Bilirubin < 2 times or Alkaline phosphatase < 4 times upper limit of normal.
12. Female participants of child-bearing potential must have a negative pregnancy test prior to treatment and agree to use dual methods of contraception for the duration of the study and for 30 days following completion of study. Male participants must also agree to use a barrier method of contraception for the

duration of the study and for 90 days following completion of study if sexually active with a female of child-bearing potential. Women who could become pregnant must have taken precautions not to become pregnant for 1 month before the start of the study. Because of the increased risk of venous thromboembolism in patients, combined oral contraceptive pills are not recommended.

13. Participants must be willing to comply with the Celgene pregnancy prevention programme for Thalidomide

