APPENDIX 2: DEFINITION OF AMYLOIDOSIS, MYELOMA AND RELATED DISEASES

Amyloid

- Tissue biopsy showing red-green birefringence in cross polarised light when stained with Congo red by Puchtler's method

Overt Non-Amyloid manifestations of Multiple Myeloma

- Lytic bony lesions (>4 if limited to skull only)
- Hypercalcaemia, hyperviscosity or plasmacytomata

Amyloid-related organ involvement causing organ dysfunction

For details please refer to Gertz et al. Definition of organ involvement and treatment response in immunoglobulin light chain amyloidosis (AL): a consensus opinion from the 10th International Symposium on Amyloid and Amyloidosis. Am J Hematol. 2005 Aug;79(4):319-28.

Defining organ involvement	
Kidney	24-hour urine protein >0.5 g per day, predominantly albumin
Heart	Echo: mean left ventricular wall thickness >12 mm, no other cardiac cause or severe diastolic dysfunction in presence of NT-ProBNP >150 pMol/L and low voltage complexes on ECG without any other cause for these abnormalities
Liver	Total liver span >15 cm in the absence of heart failure or alkaline phosphatase >1.5 times institutional upper limit of normal
Gastrointestinal tract	Symptomatic GI disturbance with or without direct biopsy verification with
Nerve	Peripheral: clinical; symmetric lower extremity sensorimotor peripheral neuropathy Autonomic: gastric-emptying disorder, pseudo-obstruction, voiding dysfunction not related to direct organ infiltration, postural hypotension
Soft tissue	Tongue enlargement, clinical Arthropathy Myopathy by biopsy or pseudohypertrophy Lymph node enlargement

Number of organs involved by amyloid

One to 5 of the following organ systems could be involved by amyloid;

- Renal
- Gastro-intestinal (including liver)
- Cardiac
- Nerves (peripheral and/or autonomic)
- Miscellaneous (e.g. significant soft tissue, factor X deficiency, adrenal insufficiency)

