5.1 General calculations

Unless otherwise stated, percentages will be calculated using the total number of patients in the appropriate population as the denominator (i.e. including all patients with missing data for that variable). All analyses will be carried out using SAS unless stated otherwise.

All percentages and means will be rounded to 1 decimal place and standard deviations to 2 decimal places. Values that are below the limit of detection and therefore non-quantifiable will be summarised using the limit of quantification value. For listings, if required, the non-quantifiable value would be reported as an inequality.

Summaries are divided into those participants treated at the recommended dose either during the dose escalation phase (prior to the identification of the recommended dose) or during the dose expansion phase (RD population), and all other participants treated during the dose escalation phase at dose levels other than the recommended dose (Non-RD population). The non-RD population will be split by dose level.

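### The organ response rate and time to organ response include patients whose only involved organ has no response criterion, or none that the scheduled tests can show; an organ-evaluable summary should stand beside the planned one.

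*Protocol*

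**What the plan says.** **Entry.** Protocol 6.3.1, criterion 2(ii), requires "Amyloid-related organ dysfunction or organ syndrome (see Appendix 2"). It does not ask for an organ that can later be scored. The organ table in Appendix 2 covers kidney, heart, liver, gut, nerve and soft tissue. Gut involvement is "Symptomatic GI disturbance with or without direct biopsy verification". Nerve involvement has two forms: "Peripheral: clinical; symmetric lower extremity sensorimotor peripheral neuropathy" and "Autonomic: gastric-emptying disorder, pseudo-obstruction, voiding dysfunction not related to direct organ infiltration, postural hypotension". A second list in Appendix 2, which counts organ systems, adds "Miscellaneous (e.g. significant soft tissue, factor X deficiency, adrenal insufficiency").

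**Scoring.** The organ response table in Appendix 4 has rows for heart, kidney, liver, nerve and soft tissue only. The whole nerve row reads "Improvement in electromyogram nerve conduction velocity (rare").

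**Schedule.** The assessment table in Protocol 11.0, the visit lists in 11.2 and the investigations in Appendix 6 contain no electromyogram or nerve conduction test, at baseline or later.

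**Denominator.** Protocol 18.3 and SAP 2.3.2 define the organ response rate as a proportion of patients, with no restriction to those who can be assessed. SAP 3.3 requires a post-baseline efficacy assessment of some kind, not an organ assessment. SAP 5.1 says that, unless otherwise stated, "percentages will be calculated using the total number of patients in the appropriate population as the denominator", and that this includes patients with missing data. Nothing different is stated for organ response. SAP 5.3.2 (secondary endpoints) adds 90% and 95% intervals, a breakdown by organ without a stated denominator, and a Kaplan-Meier analysis of time to organ response.

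**The concern.** Entry is wider than scoring. A patient whose only amyloid involvement is in the gut has no criterion for that organ. A patient with only nerve involvement has one, but the planned tests cannot show that it is met. Both stay in the denominator and in the risk set for time to organ response.

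The reported rate then mixes two things: how often a scorable organ improves, and how many enrolled patients have a scorable organ. The protocol's aims (3.1) include understanding efficacy well enough to design further trials. For that use, a later designer needs to know how many patients were assessable, and the plan does not report it.

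**Working it through.** **1. Entry organs against response rows**

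| Involvement in Appendix 2 | Where listed | Response row in Appendix 4 | Test scheduled |
|---|---|---|---|
| Heart | Organ table | Yes | Echocardiography, NT-proBNP |
| Kidney | Organ table | Yes (24-hour urinary protein) | 24-hour urine for light chains in Appendix 6; urine examinations in 6.1 |
| Liver | Organ table | Yes | Alkaline phosphatase |
| Soft tissue | Organ table | Yes (clinical or radiographic, with function) | Physical examination |
| Peripheral nerve | Organ table, defined clinically | Nerve conduction only | None |
| Autonomic nerve | Organ table, under nerve | Covered only by the nerve row | None that the row uses |
| Gut | Organ table | None | Not applicable |
| Factor X, adrenal | Counting list only | None | Factor X if indicated, with no response rule |

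Lying and standing blood pressure is scheduled, but no response rule uses it. Exclusion 8 (Protocol 6.3.2) removes severe peripheral or autonomic neuropathy only where it may interfere with adherence, so milder cases can enter.

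**2. Size**

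The plan states no organ response rate and no organ mix, so there is no planned figure to reproduce. What follows is illustrative.

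Inputs:
- n = 26: 20 expansion patients (SAP 1.4) plus the minimum of 6 treated at the dose before expansion (SAP 2.3.1), pooled under SAP 3.5. All are assumed to be in the per protocol set.
- u = number of patients with only unscorable involvement (assumed).
- p = response rate among the other patients (assumed).
- The u patients are assumed to contribute no responses.

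Reported rate = p × (n − u) / n.

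| p | u | Calculation | Reported rate |
|---|---|---|---|
| 30% | 0 | 0.30 × 26/26 | 30.0% |
| 30% | 1 | 0.30 × 25/26 | 28.8% |
| 30% | 2 | 0.30 × 24/26 | 27.7% |
| 30% | 3 | 0.30 × 23/26 | 26.5% |
| 30% | 5 | 0.30 × 21/26 | 24.2% |
| 40% | 5 | 0.40 × 21/26 | 32.3% |

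**3. Against sampling error**

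With whole patients and exact (Clopper-Pearson) 95% intervals; the choice of interval is mine, as the plan names no method:
- u = 2, 7 responders: 7/26 = 26.9% (11.6 to 47.8) for all patients; 7/24 = 29.2% (12.6 to 51.1) for scorable patients.
- u = 5, 8 responders: 8/26 = 30.8% (14.3 to 51.8) for all patients; 8/21 = 38.1% (18.1 to 61.6) for scorable patients.

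The first all-patient interval is 47.8 − 11.6 = 36.2 points wide. At p = 30% the shift is 30.0 − 28.8 = 1.2 points with one such patient and 30.0 − 24.2 = 5.8 points with five.

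**4. Time to organ response**

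The same patients enter the Kaplan-Meier analysis. With u = 5 and everyone followed equally long, half of the 26 responding means 13 events among 21 scorable patients, 13/21 = 61.9%. The median is reached later, or not at all, for a reason unrelated to treatment.

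**The case against.** **The number affected may be zero.** Only patients with no scorable organ matter; anyone who also has heart, kidney, liver or soft tissue disease can still respond. Exclusion 4 removes trivial deposits without a significant organ syndrome, and exclusion 8 narrows the nerve group. This stands: the figures above are a range of assumptions, not an estimate.

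**Zero response is not certain.** A reader might infer that these patients can never be responders. Appendix 4 does not say so. Its heart row does not require baseline heart involvement, and echocardiography and NT-proBNP are scheduled for everyone, so a gut-only patient could count as a responder on septal thickness or ejection fraction. This stands too. It makes the formula an upper bound on the dilution, and it shows a second gap: a response may be credited in an organ that was never involved.

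**Factor X and adrenal involvement.** A reader might infer that either alone qualifies a patient. They appear only as examples in the counting list of Appendix 2, and criterion 2(ii) does not say which list applies. It is a possible reading, not a stated rule.

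**Progression.** Appendix 4 likewise gives no gut row for organ progression and ties nerve progression to the same kind of test. A reader might infer that progression-free status at 6 months is affected. Neither Protocol 18.3 nor SAP 2.3.2 says that this endpoint uses organ progression, so no effect on it is shown.

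**The all-patient denominator is a legitimate choice.** SAP 5.1 is explicit and conservative, and the rate describes the population as treated. That is a good reason to keep it, but not a reason to leave out the number who could be scored. The planned breakdown by organ helps only if each organ has its own denominator. The optional sensitivity analysis in SAP 3 depends on differences in analysis-set size and would not isolate these patients.

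**Conclusion.** The point holds in limited form. The documents admit patients with only gut or only nerve involvement, give them no usable organ response criterion for that involvement, and keep them in both organ response summaries. The dilution factor is (n − u)/n if those patients contribute no responses. At n = 26 and a 30% rate in scorable patients, one to five such patients lower the reported rate to between 28.8% and 24.2%. The values of u, p and n are assumptions, and u may be zero.

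A reader might conclude that the organ response rate is useless for planning a later trial. The figures do not support that: a shift of about 1 to 6 points is small beside an interval about 36 points wide. Organ response is secondary and descriptive, activity is judged primarily on clonal response (Protocol 19.1), and no dose decision, sample size or error rate depends on it. It is still worth settling before analysis, because the remedy is cheap and a denominator chosen after seeing the data would be hard to defend.

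**What to change.** In Protocol 18.3 and SAP 2.3.2:

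1. Define an organ-evaluable set: patients with baseline Appendix 2 involvement of at least one of heart, kidney, liver or soft tissue. Nerve counts only where a baseline nerve conduction result exists.
2. Count a response only in an organ involved at baseline.
3. Report the organ response rate and time to organ response in this set, and the rate for each organ with the number of patients involved in that organ as denominator.
4. Keep the planned all-patient rate beside these, and list the patients who are not evaluable for organ response with their involved organs.

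Name the organs rather than restricting the set to whatever the scheduled tests can measure. Kidney response rests on 24-hour urinary protein, while Appendix 6 names only a 24-hour urine for light chain type and quantity, so a rule based on scheduled tests could drop kidney-only patients by accident.

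Add no new tests. The cost is a few lines of wording, one derived baseline flag, and a slightly wider interval for the evaluable-set rate, because its denominator is smaller.

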APPENDIX 5: TOXICITY CRITERIA

NCI CTCAE Toxicity Criteria (V4.03). For full list see:

http://evs.nci.nih.gov/ftp1/CTCAE/CTCAE_4.03_2010-06-14_QuickReference_8.5x11.pdf

Toxicity	1	2	3	4
CONSTIPATION	Occasional or intermittent symptoms; occasional use of stool softeners, laxatives, dietary modification, or enema	Persistent symptoms with regular use of laxatives or enemas; limiting instrumental ADL	Obstipation with manual evacuation indicated; limiting self care ADL	Life-threatening consequences; urgent intervention indicated
DIARRHOEA (patients without colostomy)	Increase of <4 stools per day over baseline; mild increase in ostomy output compared to baseline	Increase of 4 - 6 stools per day over baseline; moderate increase in ostomy output compared to baseline	Increase of ≥7 stools per day over baseline; incontinence; hospitalization indicated; severe increase in ostomy output compared to baseline; limiting self care ADL	Life-threatening consequences; urgent intervention indicated
FATIGUE	Fatigue relieved by rest	Fatigue not relieved by rest; limiting instrumental ADL	Fatigue not relieved by rest, limiting self care ADL	-
HYPOTENSION	Asymptomatic, intervention not indicated	Non-urgent medical intervention indicated	Medical intervention or hospitalization indicated	Life-threatening and urgent intervention indicated
INFECTION WITH NORMAL ANC	Asymptomatic or mild symptoms; clinical or diagnostic observations only; intervention not indicated	Moderate; minimal, local or noninvasive intervention indicated; limiting ageappropriate instrumental ADL	Severe or medically significant but not immediately lifethreatening; hospitalization or prolongation of existing hospitalization indicated; disabling; limiting self care ADL	Life-threatening consequences; urgent intervention indicated
LETHARGY	Mild symptoms; reduced alertness and awareness	Moderate symptoms; limiting instrumental ADL	-	-
MUCOSITIS:				
ANAL MUCOSITIS	Asymptomatic or mild symptoms; intervention not indicated	Symptomatic; medical intervention indicated; limiting instrumental ADL	Severe symptoms; limiting self care ADL	Life-threatening consequences; urgent intervention indicated
ORAL MUCOSITIS	Asymptomatic or mild symptoms; intervention not indicated	Moderate pain; not interfering with oral intake; modified diet indicated	Severe pain; interfering with oral intake	Life-threatening consequences; urgent intervention indicated
SMALL INTESTINAL MUCOSITIS	Asymptomatic or mild symptoms; intervention not indicated	Moderate pain; not interfering with oral intake; modified diet indicated	Severe pain; interfering with oral intake; tube feeding, TPN or hospitalization indicated; limiting self care ADL	Life-threatening consequences; urgent intervention indicated
LARYNGEAL MUCOSITIS	Endoscopic findings only; mild discomfort with normal intake	Moderate discomfort; altered oral intake	Severe pain; severely altered eating/swallowing; medical intervention indicated	Life-threatening airway compromise; urgent intervention indicated (e.g., tracheotomy or intubation)
PHARYNGEAL MUCOSITIS	Endoscopic findings only; minimal symptoms with normal oral intake; mild pain but analgesics not indicated	Moderate pain and analgesics indicated; altered oral intake; limiting instrumental ADL	Severe pain; unable to adequately aliment or hydrate orally; limiting self care ADL	Life-threatening consequences; urgent intervention indicated
TRACHEAL MUCOSITIS	Endoscopic findings only; minimal hemoptysis, pain, or respiratory symptoms	Moderate symptoms; medical intervention indicated; limiting instrumental ADL	Severe pain; hemorrhage or respiratory symptoms; limiting self care ADL	Life-threatening consequences; urgent intervention indicated
PERIPHERAL MOTOR NEUROPATHY	Asymptomatic; clinical or diagnostic observations only; intervention not indicated	Moderate symptoms; limiting instrumental ADL	Severe symptoms; limiting self care ADL; assistive device indicated	Life-threatening consequences; urgent intervention indicated
PERIPHERAL SENSORY NEUROPATHY	Asymptomatic; loss of deep tendon reflexes or paresthesia	Moderate symptoms; limiting instrumental ADL	Severe symptoms; limiting self care ADL	Life-threatening consequences; urgent intervention indicated
RASH MACULO-PAPULAR	Macules/papules covering <10% BSA with or without symptoms (e.g., pruritus, burning, tightness)	Macules/papules covering 10 - 30% BSA with or without symptoms (e.g., pruritus, burning, tightness); limiting instrumental ADL	Macules/papules covering >30% BSA with or without associated symptoms; limiting self care ADL	
NEUTROPHILS COUNT DECREASED	<LLN - 1500/mm3; <LLN - 1.5 x 10e9 /L	<1500 - 1000/mm3; <1.5 - 1.0 x 10e9 /L	<1000 - 500/mm3; <1.0 - 0.5 x 10e9 /L	<500/mm3; <0.5 x 10e9 /L
SOMNOLENCE	Mild but more than usual drowsiness or sleepiness	Moderate sedation; limiting instrumental ADL	Obtundation or stupor	Life-threatening consequences; urgent intervention indicated
THROMBOEMBOLIC EVENT	Venous thrombosis (e.g., superficial thrombosis)	Venous thrombosis (e.g., uncomplicated deep vein thrombosis), medical intervention indicated	Thrombosis (e.g., uncomplicated pulmonary embolism [venous], nonembolic cardiac mural [arterial] thrombus), medical intervention indicated	Life-threatening (e.g., pulmonary embolism, cerebrovascular event, arterial insufficiency); hemodynamic or neurologic instability; urgent intervention indicated
RESTRICTIVE CARDIOMYOPATHY	-	-	Symptomatic heart failure or other cardiac symptoms, responsive to intervention	Refractory heart failure or other poorly controlled cardiac symptoms
HAEMORRHAGE (GI)	Mild; intervention not indicated	Moderate symptoms; medical intervention or minor cauterization indicated	Transfusion, radiologic, endoscopic, or elective operative intervention indicated	Life-threatening consequences; urgent intervention indicated
HAEMORRHAGE (OTHER)	Mild; intervention not indicated	Symptomatic; medical intervention indicated	Transfusion indicated	Life-threatening consequences; urgent intervention indicated
PAIN	Mild pain	Moderate pain; limiting instrumental ADL	Severe pain; limiting self care ADL	-

APPENDIX 6: DETAILS OF INVESTIGATIONS AND THEIR TIMINGS**PLEASE ALSO SEE PROTOCOL SECTION 11**

PLEASE NOTE – prior to starting each treatment cycle at RHC a 5ml serum sample must be collected and sent to UK NAC (see protocol section 1 for contacts).

Clinical Assessments to be performed at the following timepoints:

- Baseline at UK NAC
 - Re-confirmation of Eligibility at RHC
 - Prior to each cycle at RHC
 - UK NAC visit following 3rd cycle of study treatment
 - UK NAC visit 7.5 months after start of treatment or 1 month after the end of study treatment if 6 cycles given.
- | | |
|---|---|
| 
 • Medical History at baseline • Weight • 5 minute standing blood pressure | 
 • Physical examination • Lying blood pressure • ECOG Performance Status • NYHA heart failure class |
|---|---|

Haematology to be performed at the following timepoints:

- Baseline at UK NAC
 - Re-confirmation of Eligibility at RHC
 - Prior to each cycle at RHC and at day 8 and 15
 - UK NAC visit following 3rd cycle of study treatment
 - UK NAC visit 7.5 months after start of treatment or 1 month after the end of study treatment if 6 cycles given.
- | | |
|--|---|
| 
 • Haemoglobin • Platelets • APTT | 
 • White blood count (including differential) • PT • Factor X (if indicated) |
|--|---|

Biochemistry to be performed at the following timepoints:

- Baseline at UK NAC
 - Re-confirmation of Eligibility at RHC
 - Prior to each cycle at RHC
 - UK NAC visit following 3rd cycle of study treatment
 - UK NAC visit 7.5 months after start of treatment or 1 month after the end of study treatment if 6 cycles given.
- | | |
|---|---|
| 
 • Urea • eGFR (to be calculated as per local biochemistry laboratory standard protocol) • Phosphate • ALP • AST • Bilirubin • Potassium | 
 • Creatinine (to be checked at day 8 & day 15 of each cycle) • Calcium • CRP • GGT • ALT • Albumin • Sodium |
|---|---|

APPENDIX 6 CONTINUED OVERLEAF.....

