7. The RHC will contact the patient to arrange the first RHC visit (sections 5.1 & 11.1.2), which must be within 28 days of registration, and at which eligibility for the trial must be reconfirmed

8. For patients still eligible for the trial, the RHC will fax a fully completed eligibility confirmation form to Leeds CTRU (see point 12 below). If there are any queries about eligibility, trial staff at Leeds CTRU will contact staff at the RHC immediately
9. Leeds CTRU will confirm the patient's inclusion in the trial and also confirm their registered dose level by fax to the main contact at site and the site pharmacy
10. During the dose escalation phase, the treatment start date must be confirmed and agreed with Leeds CTRU. A minimum of 15 days must have elapsed between the start of treatment of the first patient in each cohort and subsequent patients
11. For patients found to be ineligible for the trial, the RHC will fax a fully completed withdrawal form to Leeds CTRU
12. If there is a ≥ 21 day delay in starting trial treatment after completion of eligibility confirmation form at the RHC, a second eligibility confirmation form must be completed. Patients must start treatment within 6 weeks of completion of the initial eligibility confirmation form at the RHC
13. If after registration a patient decides to withdraw consent to the trial, or is found not to satisfy the eligibility criteria, the site must inform CTRU. Sites must complete a withdrawal form to confirm withdrawal details

Please see protocol section 11 for assessment summary and Appendices 6 and 7 for diagnostic sample requirements and investigations.

Once a patient has been registered onto the trial they must be provided with the following:

- A copy of their signed consent form and patient information sheet
- A patient contact card. Site on-call contact details for 24 hour medical care must be added to this card and patients advised to carry this with them at all times while participating in the trial
- A patient Red Flag card. A list of symptoms which need urgent medical attention

8. Trial Treatment

For the purpose of this protocol, the IMPs are **Carfilzomib, Thalidomide and Dexamethasone**.

All trial patients must be treated according to the following schedule in order to isolate the effects of the Carfilzomib.

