9.4 Clinical Management after Treatment Discontinuation

Patients whose underlying plasma cell dyscrasia does not respond by the end of three cycles or who have a clonal progression on treatment will be treated and followed up off trial at the discretion of the treating clinician but will have a final follow-up visit 6 months after registration.

Patients that receive 6 cycles of chemotherapy will be followed up 1 month after end of trial treatment.

Also refer to section 14 (Withdrawal of Patients) for further details regarding treatment discontinuation, patient withdrawal from trial treatment and withdrawal of consent to data collection.

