11.1.2 Assessments at RHC to reconfirm eligibility

Following consent and registration, patients will be referred by UK NAC to a Regional Haematology Centre (RHC), see section 5.1. Upon attendance at the relevant RHC, patient eligibility for the trial will be reconfirmed by the treating Haematologist. This visit must be within 28 days of registration. The following investigations and assessments will be carried out by the RHC to confirm eligibility of the patient for the trial:

- Physical examination
- FBC (including Hb, White Cell Count, Platelets), clotting screen (PT, APTT, Factor X (if indicated)), biochemistry (including creatinine, eGFR, calcium, phosphate, CRP, ALP, GGT, AST, ALT, bilirubin, albumin, sodium, potassium)
- Pregnancy test

For all patients who still fulfil the eligibility criteria for the trial, the RHC must complete the eligibility confirmation form and fax to LEEDS CTRU. LEEDS CTRU will confirm patient's entry into trial and upon receipt of this at RHC, the patient will receive the protocol treatment regimen.

If there is a ≥ 21 day delay of reconfirmation of eligibility, the RHC will have to carry out the above investigations and assessments again and complete another eligibility confirmation form, to allow the patient to continue on the trial. If the patient is unable to start treatment within 6 week of completion of the first eligibility confirmation form completed by the RHC, he/she will be withdrawn from the trial.

Patients who are no longer eligible for the trial will be withdrawn from the trial and treated according to standard local practice (the RHC site staff will complete the Withdrawal Form and fax to LEEDS CTRU).

LEEDS CTRU will inform UK NAC of all patients entering/withdrawing from the trial at this point.

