11.3 Assessments during follow up

Follow up investigations will be carried out at 6 months after registration or one month after the last cycle of chemotherapy, if all 6 cycles were received, as detailed in the Assessment Summary table in section 11.0.

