APPENDIX 6 CONTINUED FROM PREVIOUS PAGE

Other investigations to be performed at UK NAC at the following timepoints:

- PLEASE NOTE – prior to starting each cycle at RHC a 5ml serum sample must be collected and sent to UK NAC
- * Baseline at UK NAC, at UK NAC visit following 3rd cycle of study treatment, at UK NAC visit 6 months after registration or 1 month after the end of study treatment if 6 cycles given and on posted serum samples and on each posted sample sent by RHC as defined in protocol
- ** Baseline visit to UK NAC and at UK NAC visit 6 months after registration or 1 month after the end of study treatment if 6 cycles given. Bone marrow tests will be done at these time points only if clinically indicated.
- *** Baseline at UK NAC, at UK NAC visit following 3rd cycle of study treatment, at UK NAC visit 6 months after start of treatment or 1 month after the end of study treatment if 6 cycles given. At RHC ECHO will be done at end of cycle 2 only. Echocardiogram to be repeated at any cycle if clinically indicated for unexpected worsening of cardiac function.
- **** Baseline at UK NAC, 1st cycle of treatment at day 1, 8 & 15 at RHC, day 1 of every subsequent cycle at RHC, at UK NAC visit following 3rd cycle of study treatment, at RHC at end of treatment, visit, at UK NAC visit 6 months after registration or or 1 month after the end of study treatment if 6 cycles given.
 - Serum Free Light Chains*
 - NT-ProBNP****
 - Echocardiography ***
 - Bone marrow aspirate & trephine plasmacytosis**
 - 24 hour urinary light chain type and quantification**
 - Serum monoclonal protein*

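### For patients who stop before six cycles, Appendix 6 sets three final assessment times that conflict with the single visit in sections 9.4 and 11; read literally, it puts final biochemistry 1.5 to 3.8 months after the 6-month organ-response window

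*Protocol*

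**What the plan says.** **Body of the Protocol.** Section 9.4 states that patients who have not responded after three cycles, or who progress clonally on treatment, "will have a final follow-up visit 6 months after registration". Section 11.3 says: "Follow up investigations will be carried out at 6 months after registration or one month after the last cycle of chemotherapy", the second option being for those who received all six cycles. Sections 11.0 and 11.2 agree. The section 11.0 table has a single follow-up column at the UK NAC that holds physical examination, laboratory tests, response assessment and echocardiography together.

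**Appendix 6.** For patients with fewer than six cycles it gives three times:

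- Clinical assessments, haematology and biochemistry (including creatinine, eGFR and alkaline phosphatase): "UK NAC visit 7.5 months after start of treatment or 1 month after the end of study treatment if 6 cycles given". The line appears under each of the three lists.
- Echocardiography: "at UK NAC visit 6 months after start of treatment or 1 month after the end of study treatment if 6 cycles given".
- NT-proBNP: "at UK NAC visit 6 months after registration or or 1 month after the end of study treatment if 6 cycles given". Light chains, serum monoclonal protein, marrow and 24-hour urine also run from registration.

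**Endpoint.** Protocol section 18.3 and SAP section 2.3.2 count organ response within 3 and within 6 months of registration.

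**The concern.** The same final visit has different dates depending on which page a site reads, and Appendix 6 alone spreads its components over up to three dates. The laboratory-tests footnote to the section 11.0 table refers sites to Appendix 6, and section 11 and Appendix 6 each point to the other. Neither is given precedence, so a site can comply with one and breach the other.

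At stake is the organ-response rate within 6 months. If biochemistry is timed from start of treatment while the endpoint is timed from registration, an early stopper's last alkaline phosphatase and creatinine fall outside the window they are meant to inform. The last NT-proBNP would also be judged against renal function measured at another time. How much final-visit data enters the endpoint would then depend on which text the site followed.

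**Working it through.** **Inputs**

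- Registration to the visit at the regional centre: at most 28 days (section 11.1.2: "This visit must be within 28 days of registration").
- Eligibility form to first dose: at most 42 days (section 7.1: "Patients must start treatment within 6 weeks of completion of the initial eligibility confirmation form at the RHC").
- Assumption: the form is completed at that visit.
- One month = 30.44 days.

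**The plan's own figure.** The documents give no derivation for 7.5 months, and it does not follow from the schedule. Six 28-day cycles are 168 days = 5.52 months, and adding 1 month gives 6.52 months from first dose.

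**Lag from registration to first dose.** Maximum L = 28 + 42 = 70 days; 70 / 30.44 = 2.30 months.

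**Appendix 6 dates, in months from registration**

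- Clinical, haematology, biochemistry: L + 7.5
- Echocardiography: L + 6
- Light chains, paraprotein, NT-proBNP, urine: 6, whatever L is

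| Lag (days) | Biochemistry | Echocardiography | NT-proBNP | Biochemistry beyond 6 months |
|---|---|---|---|---|
| 0 | 7.50 | 6.00 | 6.00 | 1.50 |
| 28 | 8.42 | 6.92 | 6.00 | 2.42 |
| 42 | 8.88 | 7.38 | 6.00 | 2.88 |
| 70 | 9.80 | 8.30 | 6.00 | 3.80 |

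The 3.80 becomes 3.76 with 31-day months and 3.83 with 30-day months. Under section 11 the overshoot is 0, because every item belongs to one visit at 6 months after registration.

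**Which criteria in Appendix 4 are touched**

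- *Liver response:* a fall in alkaline phosphatase is one of two alternatives, and under Appendix 6 its final value always falls after the window.
- *Heart response:* the NT-proBNP alternative carries a condition on renal function. NT-proBNP would be dated 6.0 months and the final renal function 7.5 to 9.8 months.
- *Kidney response:* urinary protein loss is combined with creatinine clearance, so the same mismatch would arise. This pairing is inferred, since Appendix 6 lists 24-hour urinary light chain quantification and not urinary protein.
- *Clonal response:* light chains and paraprotein both run from registration, so it is untouched.
- *Primary endpoints:* dose-limiting toxicity in cycle 1 and grade 3 or 4 toxicity during treatment do not use the final visit.

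**Six-cycle completers, for comparison.** Their final visit is 168 days + 1 month = 6.52 months after first dose. Adding 0 to 2.30 months of lag gives about 6.5 to 8.8 months after registration.

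**The case against.** The strongest reply is that section 11 and section 9.4 are clear, that most Appendix 6 footnotes already use 6 months after registration, and that a site working from the section 11.0 table has no gap. The 3.8 months also needs both the longest permitted lag and a literal reading of the appendix. This limits the size but does not remove the conflict. The 7.5-month line stands three times in current text, the section 11.0 footnote sends sites to it, and even with no lag it is 1.5 months late.

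Several stronger readings are tempting, and the documents do not support them.

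- *That 6-month data would be missing selectively in early stoppers.* Completers are also seen after 6 months, at about 6.5 to 8.8 months. Early stoppers have an end-of-treatment visit with laboratory tests and NT-proBNP, biochemistry before each cycle, and, if they reach it, the UK NAC assessment after cycle 3. Because response within 6 months is cumulative, those values count.
- *That heart response needs echocardiography and NT-proBNP together.* Appendix 4 joins the heart criteria by alternatives, each sufficient alone. Their different dates break no paired rule; only the renal condition on NT-proBNP does.
- *That progression at 6 months is distorted.* Neither section 18.3 nor SAP section 2.3.2 defines progression. Any effect assumes the Appendix 4 organ criteria are used.
- *That the number of affected patients can be estimated from the cited AL amyloidosis study.* Its response rate is 7 of 9 (exact 95% interval about 40% to 97%), on a twice-weekly regimen without thalidomide. That is too thin a basis for a count.
- *That the late values would miss the final analysis.* Protocol section 19.5 and SAP section 1.5 set it after at least 6 months from registration, but SAP section 6 places it after the last participant's last data item.

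**Conclusion.** The point holds as an internal inconsistency with a limited effect. For patients given fewer than six cycles, Appendix 6 read literally places final biochemistry 1.5 to 3.8 months after the 6-month organ-response window and echocardiography 0 to 2.3 months after it. If section 11 is followed, both figures are zero.

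The range rests on the Protocol's own limits for starting treatment and on the eligibility form being completed at the regional visit. The explicit consequences are for the final alkaline phosphatase in liver response and for renal function as a condition on the NT-proBNP heart criterion. The kidney consequence is inferred. Organ response is secondary and descriptive, activity is judged primarily by clonal response, and sample size is unaffected. It should still be corrected, because a stated rule conflicts with the endpoint's time origin and the activity data are meant to inform the design of further trials.

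**What to change.** 1. Reconcile Appendix 6 with sections 9.4, 11.0, 11.2 and 11.3. For patients who stop before six cycles, give every final-visit item (clinical, haematology, biochemistry, echocardiography, light chains, paraprotein, NT-proBNP, urine) one common time and one visit window, counted from registration as the 6-month endpoints in section 18.3 are.
2. In section 18.3 and SAP section 2.3.2, state how final-visit values obtained later than 6 months after registration count towards the 6-month endpoints. This must cover six-cycle completers, whose final visit falls after 6 months under either text.

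The cost is wording in the appendix and a sentence in each of the two endpoint sections. No assessment is added, the sample size does not change, and early stoppers may be spared duplicate attendances at the UK NAC.
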